### **GPI negative neutrophil level**

Shift tables using GPI negative neutrophil and RBC level ( $\leq 50\%$  and  $> 50\%$ ) to compare baseline to the worst on-treatment will be presented.

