5.2 Exclusion criteria

Participants meeting any of the following criteria are not eligible for inclusion in this study.

1. Prior IST with any ATG/ALG, alemtuzumab, high dose cyclophosphamide ($\geq 45 \text{ mg/kg/day}$), CsA within 6 months, or prior thrombopoietin receptor (TPO-R) agonists
2. Participants have an Eastern Cooperative Oncology Group (ECOG) performance status (age ≥ 16 years) > 2 , or Lansky performance status (age < 16 years) < 50
3. Prior and/or active medical history of:
 - Known underlying congenital/inherited bone marrow failure or aplastic anemia (such as but not limited to Fanconi anemia, congenital dyskeratosis, congenital amegakaryocytic thrombocytopenia, or Shwachman-Diamond Syndrome)
 - Symptomatic paroxysmal nocturnal hemoglobinuria (PNH) and/or PNH clones $> 50\%$ of polymorphonuclear neutrophil or RBC at time of enrollment
 - Myelodysplastic syndrome
 - Any cytogenetic abnormalities on karyotyping or fluorescence in situ hybridization (FISH) within 30 days of study enrollment (an evaluable karyotyping with at least 10 metaphases is mandatory for eligibility)
 - Other known or suspected underlying primary immunodeficiency
 - Any concomitant malignancies that have not fully recovered from treatment or have not been disease-free for 5 years
4. Aspartate aminotransferase (AST) or alanine aminotransferase (ALT) > 3 times the upper limit of normal (ULN)
5. Creatinine $\geq 2.5 \times$ local ULN
6. Past medical history of thromboembolism within 6 months and/or prior or current antiphospholipid antibody syndrome (APS)
7. Presence of clinically active uncontrolled significant (of such severity that it would preclude the participant's ability to consent, be compliant with study procedures, tolerate protocol therapy) infection, including bacterial, fungal, mycobacterial, parasitic or viral infection, or any concurrent condition that, in the Investigator's opinion, would jeopardize the safety of the participant or compliance with the protocol
8. Any severe and/or uncontrolled medical conditions which could cause unacceptable safety risks or compromise compliance with the protocol, such as:
 - Known hepatocellular disease (e.g. active hepatitis or cirrhosis)
 - Impairment of gastrointestinal (GI) function or gastrointestinal disease that may significantly alter the absorption of study treatment (e.g., ulcerative disease, uncontrolled nausea, vomiting, diarrhea, malabsorption syndrome)

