8.4.4 Evaluation of clonal evolution

Cytogenetic abnormalities will be assessed during the whole study. For all participants, regardless of disposition, the assessments will be monitored at Week 13, Week 26, Week 52 and yearly after, and when clinically indicated.

Cytogenetic abnormalities will be assessed by karyotyping (G-banding) and FISH (for example, probes targeting abnormalities in chromosome 3, 5, 7, 8 and those associated with SAA, MDS, AML etc).

Detection of PNH and measurement of PNH granulocyte clone size measurement by flow cytometry will be done at screening period. If persistently negative, it will be monitored every 6 months up to Year 2 (Week 104) and then Year 3 (Week 156) unless symptoms or signs develop. If the PNH screen is, or becomes positive, it will be tested every 3 months and only reduce the frequency if the proportion of the PNH cells has remained stable ([Killick et al 2016](#)).

Clonal evolution to AML and MDS will also be monitored during the study period, and relevant examinations will be done when clinically indicated.

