3. its duration (start and end dates) or if the event is ongoing, an outcome of not recovered/not resolved must be reported
4. whether it constitutes a SAE (see [Section 10.1.2](#) for definition of SAE) and which seriousness criteria have been met
5. action taken regarding with study treatment

All AEs must be treated appropriately. Treatment may include one or more of the following:

- Dose not changed
- Dose Reduced/increased
- Drug interrupted/withdrawn
- Its outcome

1. not recovered/not resolved;
2. recovered/resolved;
3. recovered/resolved with sequelae;
4. fatal; or unknown.

If the event worsens, the event should be reported a second time in the CRF noting the start date when the event worsens in toxicity. For grade 3 and 4 AEs only, if improvement to a lower

grade is determined a new entry for this event should be reported in the CRF noting the start date when the event improved from having been Grade 3 or Grade 4.

Conditions that were already present at the time of informed consent should be recorded in medical history of the participant.

AEs (including lab abnormalities that constitute AEs) should be described using a diagnosis whenever possible, rather than individual underlying signs and symptoms.

AE monitoring should be continued for at least 30 days following the last dose of eltrombopag.

Once an AE is detected, it must be followed until its resolution or until it is judged to be permanent (e.g. continuing at the end of the study), and assessment must be made at each visit (or more frequently, if necessary) of any changes in severity, the suspected relationship to the interventions required to treat it, and the outcome.

Information about adverse drug reactions for the investigational drug can be found in the eltrombopag Investigator's Brochure.

Abnormal laboratory values or test results constitute AEs only if they fulfill at least one of the following criteria:

- they induce clinical signs or symptoms
- they are considered clinically significant
- they require therapy

Clinically significant abnormal laboratory values or test results must be identified through a review of values outside of normal ranges/clinically notable ranges, significant changes from baseline or the previous visit, or values which are considered to be non-typical in participants with the underlying disease.

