### **Baseline**

For safety and efficacy evaluations, the last available assessment on or before the date of start of study treatment is defined as “baseline” assessment.

For ECG assessment, the average of the triplicate assessment should be used as baseline.

If patients have no value as defined above, the baseline result will be missing.

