## **2.12 Cytogenetic abnormalities and clonal evolution**

### **Cytogenetic abnormalities and clonal evolution observed during the study**

Cytogenetic abnormalities and clonal evolution will be selected from AE page in eCRF, and will be chosen as AE Preferred term = “clonal evolution / cytogenetic abnormality / AML / MDS / PNH”.

Clonal cytogenetic evolution will be evaluated during the study, and the rate of the subjects who developed any clonal evolution (e.g., clonal evolution to PNH, evolution to AML or MDS etc.) will be calculated in a summary table. Short narratives and relevant information for subjects with new cytogenetic abnormalities on study will be listed.

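### The GPI-negative clone shift table has a single cut at 50%, the entry limit, so it only counts clones that passed 50% on treatment; smaller new or growing clones reach a summary only if reported as adverse events

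*SAP*

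**What the plan says.** The primary-analysis SAP (2.12, GPI negative neutrophil level) and the final-analysis SAP (2.11, same subheading) plan "Shift tables using GPI negative neutrophil and RBC level" in two categories, at or below 50% and above 50%, "to compare baseline to the worst on-treatment will be presented". Baseline is defined in SAP 2.1.1: "the last available assessment on or before the date of start of study treatment is defined as “baseline” assessment".

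Protocol 5.2, criterion 3, excludes "Symptomatic paroxysmal nocturnal hemoglobinuria (PNH) and/or PNH clones" above 50% of neutrophils or red cells at enrollment.

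For clonal evolution, PNH included, both SAPs state that cases "will be selected from AE page in eCRF" by preferred term, and the rate of affected participants is tabulated from that selection.

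Protocol 8.4.4 measures PNH clone size by flow cytometry at screening and then repeatedly: "If the PNH screen is, or becomes positive, it will be tested every 3 months". Persistently negative participants are tested every 6 months to Week 104 and again at Week 156.

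Protocol 12.5.2 plans a summary of clonal evolution to PNH at each planned visit, with number, percentage and exact 95% confidence interval, and does not tie it to adverse event reports.

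**The concern.** A shift table should show movement between meaningful states. Here the only boundary is the value that would have kept the participant out of the trial, so the upper baseline row is empty by design and movement within the whole eligible range cannot be seen.

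The adverse-event rate is a weak substitute because it depends on what each site chose to report. Protocol 10.1.1 says: "Abnormal laboratory values or test results constitute AEs only if they fulfill at least one of the following criteria". The criteria are that the result causes signs or symptoms, is considered clinically significant, or requires therapy. The explicit duty to record applies to new cytogenetic abnormalities. Section 8.4.4 assesses those by karyotyping and FISH, and handles PNH separately by flow cytometry.

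Clonal evolution is a secondary objective in a study meant to support registration. A report could show no shifts and few or no PNH events while GPI-negative clones emerged or grew below 50%, and its summaries would not reveal this.

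**Working it through.** No sample size or error rate is involved, and the plan states no figure to reproduce. The check is an enumeration of the table and a search for any other planned summary that would fill the gap.

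**1. Baseline rows.** Eligible means a clone of 0% to 50%. The lower category is 0% to 50%. On a 1% grid, all 51 eligible baseline values (0, 1, …, 50) fall in the lower row and none in the upper. An upper-row baseline can arise only from an eligibility deviation, or if the clone changed between the enrollment test and the last test before treatment.

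**2. What counts as a shift.** The finer cuts in the last column (1%, 10%, 50%) are assumed for illustration and are not in the documents.

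| Baseline → worst | Planned cut at 50% | Illustrative finer cuts |
|---|---|---|
| 0% → 1% | no shift | shift |
| 0% → 10% | no shift | shift |
| 0% → 25% | no shift | shift |
| 0% → 50% | no shift | shift |
| 0% → 51% | shift | shift |
| 49% → 51% | shift | shift |

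A rise of 50 percentage points (50 − 0) can be invisible, while a rise of 2 points (51 − 49) is counted. With one baseline row occupied, the table carries one number: participants whose clone exceeded 50% on treatment.

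**3. Time span.** On-treatment ends 30 days after the last eltrombopag dose (SAP 2.1.1). Eltrombopag is provided up to Week 52, Day 365 in protocol Table 8-1, so the window closes at about Day 365 + 30 = Day 395, or earlier for those who stop sooner. PNH testing runs to Year 3, Day 1093. A clone first seen after the window misses this table even if it is above 50%.

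**4. Other planned summaries.**
- The hematology and chemistry shift tables (SAP 2.8.3) do not cover it. Protocol Table 8-3 lists peripheral-blood flow cytometry as a separate test category.
- The bone marrow examination listings (SAP 2.8.4.3) do not include peripheral-blood flow cytometry.
- The clonal-evolution rate uses adverse event preferred terms only.
- Neither SAP's methods describe a time-to-event analysis of clonal evolution, although Table 1-1 of both still lists that endpoint.
- SAP 2.1.1 lists all safety data, so individual clone sizes should appear in listings. A listing gives no count, rate or interval.

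**5. Protocol against SAP.** Protocol 12.5.2 has a per-visit n, % and exact CI, with no restriction to adverse events. The SAPs have an adverse-event rate plus the 50% table. Section 4 of each SAP, on changes to protocol-specified analyses, names only added efficacy endpoints.

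**6. What a flow-based count would look like.** With assumed numbers of new clones among 36 participants, the Clopper-Pearson 95% intervals are:
- 1/36 = 2.8% (0.1, 14.5)
- 3/36 = 8.3% (1.8, 22.5)
- 5/36 = 13.9% (4.7, 29.5)

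These are imprecise, but they can be reported in the form protocol 12.5.2 calls for.

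**The case against.** The best case for the plan has four parts.

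First, no passage defines clonal evolution to PNH as any detectable GPI-negative clone. Section 8.4.4 refers to a screen turning positive only to set how often to test. This stands. A reader might infer that the report would understate clonal evolution to PNH, but that presumes a definition the documents do not give.

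Second, adverse event capture is ambiguous rather than absent. A result judged clinically significant qualifies without symptoms or treatment, and 10.1.1 also states an aim of tracking all evidence of clonal evolution, with non-serious events entered in the eCRF. A site could well report a new clone on that basis. This also stands: a reader might infer that sub-50% clones would go unreported, and the documents do not establish that. What remains is that no rule says when a flow result becomes an event, so the count rests on site judgement although quantitative data exist.

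Third, individual values should be in the listings, and with about 36 participants a trajectory could be read there. That is correct, and it means the data are not lost. It does not supply the summary that 12.5.2 plans.

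Fourth, showing who newly exceeds the entry limit is a legitimate descriptive choice in a single-arm study with no formal testing. It is, and that count can stay. As the only summary taken from the flow-cytometry data, it uses almost none of the information collected.

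**Conclusion.** The point holds as a weakness in a descriptive safety summary and as an undeclared narrowing of protocol 12.5.2. Apart from eligibility deviations, missing baselines or a change between enrollment and baseline, every baseline sits in one row, and the table is a single count of clones above 50% on treatment. A clone that emerges or expands below 50% enters no planned summary unless the investigator reports it as an adverse event, which 10.1.1 does not clearly require. Individual values would be visible only in listings.

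How many participants this affects cannot be known from the documents. The conclusion rests on the SAP being followed as written and on flow cytometry being performed as 8.4.4 describes. It does not rest on treating every detectable clone as PNH, and it does not touch the primary endpoint.

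**What to change.** In SAP 2.12 and final-analysis SAP 2.11:

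- Add categories below 50%: at least negative versus positive by the assay's limit, and one intermediate cut. The sponsor should prespecify the values, since the documents give neither. Keep the 50% cut as the top boundary.
- Compare baseline with the worst post-baseline value through Year 3, not only the on-treatment period.
- From the flow-cytometry data, report n (%) with exact 95% CI of participants negative at screening and positive later.
- Label these results as new or expanding GPI-negative clones and show them beside the adverse-event rate, without renaming every detectable clone as clonal evolution to PNH.
- Summarise at each planned visit as 12.5.2 states, or declare the departure in section 4 of each SAP.

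The cost is SAP wording and one reprogrammed table from data the protocol already collects. The drawback is small cell counts.

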## 2.13 Other Exploratory analyses

The exploratory analysis is PK/PD relationships, for details, please see [section 2.10](#).

## 2.14 Interim analysis

No formal interim analysis is planned for this trial. The primary analysis will be performed after all subjects have completed Week 26 or discontinued prior to Week 26. A final analysis will be performed after all subjects have completed the study. No formal testing of the primary endpoint will be performed in this study.

# 3 Sample size calculation

As this is a bridging study to support registration, an estimation strategy rather than formal hypothesis testing will be pursued. Approximately 36 subjects will be enrolled into the study based on the feasibility rather than statistical considerations. This number of subjects is considered appropriate to assess the efficacy and safety of eltrombopag in Asian patients.

## 3.1 Primary analysis

Based on the Day 120 report in the pivotal study of CETB115AUS01T, the complete hematological response rate at Month 6 in Cohort 3+Extension is 43.7%. If the CR rate obtained in naive Asian patients with SAA treated with eltrombopag is expected to be 44.0%, a total of 36 subjects will result in a 95% CI lower bound of about 28%.

Below table shows the exact 95% CIs for various observed complete hematological response rate. The maximum half-width of the 95% CIs is 17.1%.

**Table 3-1 95% CIs for various observed response rate**

Total sample size	# of responders	Complete hematologic response rate (%)	95% CI (%)
36	14	38.9	(23.1, 56.5)
36	16	44.4	(27.9, 61.9)
36	18	50.0	(32.9, 67.1)

The 12 evaluable subjects for intensive PK sampling was chosen based on feasibility and practical considerationzs to assist in characterizing the PK of eltrombopag in Chinese subjects.

## 3.2 Power for analysis of key secondary variables

Not Applicable

# 4 Change to protocol specified analyses

Below-listed endpoints were added to further support efficacy analysis beyond protocol.

- Time to response
- Maximum duration of Platelet and RBC transfusion free

- Proportion of subjects with transfusion decrease
- Changes in platelet count, hemoglobin and neutrophil count

## 5 Appendix

### 5.1 Imputation rules

#### 5.1.1 Study drug

The following rule should be used for the imputation of the dose end date for a given study treatment component:

**Scenario 1:** If the dose end date is completely missing and there is no EOT page and no death date, the patient is considered as on-going:

The patient should be treated as on-going and the cut-off date should be used as the dose end date.

**Scenario 2:** If the dose end date is completely or partially missing and the EOT page is available:

Case 1: The dose end date is completely missing, and the EOT completion date is complete, then this latter date should be used.

Case 2: Only Year(yyyy) of the dose end date is available and yyyy < the year of EOT date:

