This is a non-randomized, open label, single arm, multi-center, Phase II study to evaluate the efficacy and safety of eltrombopag in combination with IST regimen of r-ATG + CsA in East-Asian patients with SAA who have not received prior IST. At least 36 participants will be enrolled from China, Japan, Korea or Taiwan. At least 6 pediatric participants will be recruited in total, with 3 participants from China and 3 from Japan respectively. At least one of the 6 pediatric participants in each age group (6 to 11 years old, and 12 to 17 years old) will be enrolled. For the 30 adult participants, at least 12 participants will be recruited from China to fulfill the requirements for pharmacokinetic (PK) profile.

Figure 3-1 Study design

Eligible participants will be enrolled into the study and will receive eltrombopag (from Day 1 to Week 26) concomitantly with r-ATG (on Days 1-5) and CsA (from Day 1 to Week 26) in the core treatment part.

Efficacy assessments will be performed at Week 13 and Week 26 in the core treatment part of the study.

Participants who are assessed as responders (meeting CR or PR criteria) at Week 26 are eligible to the extension part of the study and continue treatment with eltrombopag and CsA after Week 26.

Study treatment should be discontinued if the participant is not assessed as a responder at Week 26.

During the extension part, eltrombopag treatment will be provided up to Week 52. CsA will be maintained or tapered at the investigator's discretion according to local practice, with a total duration of at least 2 years (18 months after Week 26, see [Section 6.1.5](#)). End of treatment (EOT) assessments will be performed after eltrombopag discontinuation at anytime during the study. After that, safety follow-up visit will be performed 30 days after the discontinuation of eltrombopag, and participants will enter the long-term follow-up part, with yearly efficacy and clonal evolution assessments up to Year 3 (Week 156).

For non-responders at Week 26, and participants who relapse or receive alternative SAA treatment, safety follow-up visit will be performed 30 days after the discontinuation of eltrombopag, and then clonal evolution and survival will continue to be followed up to Year 3 (Week 156).

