6.1.5 Treatment duration

The core treatment part of this study is 6 month from the start of eltrombopag treatment (Day 1 to Week 26). Participants assessed as responders at Week 26 will be eligible to enter the extension part and may continue treatment with eltrombopag and CsA after Week 26 until Week 52.

Core treatment part

The planned duration of eltrombopag treatment is 6 months in the core treatment part. Participants may be discontinued from treatment earlier due to unacceptable toxicity, disease progression and/or treatment is discontinued at discretion of the investigator or of the participant (see [Section 9.1.1](#)).

The administration of r-ATG will be from Day 1 to Day 5.

For all participants, CsA will be administered at doses that obtain the target trough level range for 6 months if well tolerated. CsA dose may be interrupted temporarily when clinically indicated at the discretion of the investigator or treating physician. The parenteral route of administration may be used temporarily for CsA administration if indicated. Temporary interruptions for transient toxicities or dose adjustments will be reported. Per protocol interruptions will not be reported as deviations.

Extension part

The participants assessed as responders at Week 26 are eligible to enter the extension part. Eltrombopag will be provided up to Week 52 for the participants who enter the extension part and are considered to require continued treatment. For the participants who meet the discontinuation criteria in [Section 9.1.1](#), the study treatment will be discontinued.

In extension part, CsA will last for at least 18 months after Week 26 if well tolerated (total duration is from Day 1 to at least Year 2). CsA will be maintained or tapered based on the discretion of the investigator according to local practice. It is recommended that CsA treatment dose last for at least 3 months after achieving the best hematologic response, and after that CsA is recommended to be tapered by 0.3 mg/kg every month or 1 mg/kg every 3 months. CsA dose may be decreased or interrupted temporarily when clinically indicated at the discretion of the investigator or treating physician. Temporary interruptions for transient toxicities or dose adjustments will be reported. Per protocol interruptions will not be reported as deviations. After Year 2 (Week 104), CsA administration will be at the discretion of the investigator, and will not be provided within the trial anymore.

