#### **Study treatment**

Study treatment includes any of the following: r-ATG, CsA, eltrombopag or combination of these drugs administered to the patient as part of the required study procedures up to the end of Year 2.

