**Use last day of the Month (mm)**

All other cases should be considered as a data issue.

After imputation, compare the imputed date with start date of treatment, if the imputed date is < start date of treatment: Use the treatment start date

Patients with missing start dates are to be considered missing for all study treatment component related calculations and no imputation will be made. If start date is missing then end-date should not be imputed.

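### A missing dose end date for any drug is filled with the EOT date, but EOT here marks the end of eltrombopag, so an open CsA record in a participant past EOT is closed too early

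*SAP*

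**What the plan says.** SAP Section 5.1.1 opens with its scope: "The following rule should be used for the imputation of the dose end date for a given study treatment component". The SAP's general definitions list the components: "Study treatment includes any of the following: r-ATG, CsA, eltrombopag or combination of these drugs". No component is excepted.

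- **Scenario 1** applies "If the dose end date is completely missing and there is no EOT page and no death date". Its instruction is: "The patient should be treated as on-going and the cut-off date should be used as the dose end date".
- **Scenario 2** applies once an EOT page is available. Case 1 reads: "The dose end date is completely missing, and the EOT completion date is complete, then this latter date should be used". Case 3 also uses the EOT date, when only the year of the dose end date is known and it equals the EOT year.
- **Check after imputation.** There is only a lower bound: "if the imputed date is < start date of treatment: Use the treatment start date".

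The final-analysis SAP (11-Nov-2024) repeats all of this in its own Section 5.1.1.

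Protocol Section 3 ties EOT to one drug: "End of treatment (EOT) assessments will be performed after eltrombopag discontinuation at anytime during the study". Section 1.1 of both SAPs agrees. Protocol Section 6.1.5 provides eltrombopag up to Week 52 and r-ATG on Days 1 to 5. It continues CsA in responders for at least 18 months beyond Week 26 if tolerated, and adds: "After Year 2 (Week 104), CsA administration will be at the discretion of the investigator". Table 8-1 shows CsA prescribed monthly up to Year 2 in the follow-up columns, except for participants who stopped eltrombopag for non-response at Week 26, relapse or alternative SAA treatment.

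**The concern.** The rule treats EOT as the end of all treatment, but the protocol plans for CsA to outlast EOT by a year or more. A responder who has finished eltrombopag and is still on CsA has a completed EOT page and, for the current CsA record, no end date. That is Scenario 2, Case 1. Scenario 1, the only rule for ongoing treatment, is closed to this participant because an EOT page exists.

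Section 2.4.1 of both SAPs plans duration of exposure per component, with CsA time categories up to 24 months. An error that always shortens CsA misdescribes a background drug whose planned two-year course is part of the regimen under study. The same wording also reaches r-ATG, in the opposite direction.

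**Working it through.** The plan gives no figure that depends on this rule, so there is none to reproduce. As a check on the calendar, visit day = 7 × week + 1 gives Week 26 = Day 183, Week 52 = Day 365 and Week 104 = Day 729, all matching Table 8-1.

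**Formulas.** From SAP 2.4.1, duration = last date − first date + 1. From SAP 2.1.1, months = days / 30.4375.

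**Inputs and assumptions**
- The last participant's first visit was 03-Dec-2021 (protocol, Amendment 3). Adding 26 weeks (182 days) gives 3-Jun-2022.
- The primary-analysis SAP is dated 1-Jul-2022, before database lock. The cut-off itself is not stated. I assume 3-Jun to 1-Jul-2022.
- Start dates are not given. Three participants were enrolled by 08-Dec-2020 (Amendment 2), so 1-Dec-2020 is an assumed early start. 1-Mar-2021 is a second illustration.
- EOT is at Day 365, the latest planned.

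**CsA at the primary cut-off, worst case** (one open record, unchanged since before EOT)

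| Start | Days on CsA at cut-off | Recorded under Case 1 | Lost |
|---|---|---|---|
| 1-Dec-2020 | 550 to 578 (18.1 to 19.0 months) | 365 (12.0 months) | 185 to 213 days (33.6% to 36.9%) |
| 1-Mar-2021 | 460 to 488 (15.1 to 16.0 months) | 365 (12.0 months) | 95 to 123 days (20.7% to 25.2%) |

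The first participant drops from the 18-to-24-month category to the 6-to-12-month category, and the second from 12-to-18 to 6-to-12. An EOT before Week 52 with CsA continuing would lose more.

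**CsA with later closed records.** Closed records keep their dates, so only the time since the open record began is lost. Protocol 6.1.5 recommends taper steps every month or every 3 months. If records are closed at those steps (my assumption), the loss is at most about 30 or 91 days. Of 550 days that is 30/550 = 5.5% or 91/550 = 16.5%.

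**CsA at the final analysis.** If an end date were still missing, the planned course to Year 2 (729 days, 23.95 months) would become 365 days, a loss of 364 (50%). With EOT at Week 26 it would become 183 days, a loss of 546 (75%). These are bounds for a record left open a year after trial supply ended, not expected values.

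**r-ATG.** A course of 5 days becomes 183 or 365 days, that is 36.6 or 73 times as long. The protocol range of 2.5 to 3.5 mg/kg/day gives a total of 12.5 to 17.5 mg/kg. Dividing by 183 gives 0.07 to 0.10 mg/kg/day; dividing by 365 gives 0.03 to 0.05. Without an EOT page, Scenario 1 runs the course to the cut-off. The lower-bound check catches none of this.

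**Does other text rescue the rule?** SAP 2.1 says events without an end date are shown as ongoing and not imputed, but for exposure it names eltrombopag only. A partial CsA end date in a year after the EOT year matches none of the four cases and is treated as a data issue, which suggests the rule assumes no drug outlasts EOT. Neither document describes a separate EOT page for CsA or r-ATG.

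**The case against.** The strongest reply is that the rule touches only missing or year-only dates. CsA dose adjustments are reported, prescription is monthly, and every closed record after EOT keeps its true date. Study-supplied CsA ends at Week 104 while follow-up runs to Week 156, so nearly all records should be closed by the final lock. r-ATG is infused in hospital under supervision and missing values are queried, so a blank r-ATG end date surviving to lock is unlikely. The eCRF is not shown, and an EOT page specific to each drug would remove the problem. Finally, these are descriptive exposure tables.

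Most of this stands as a limit on size. It does not cure the rule: for an ongoing CsA record a blank end date is the normal state, and both documents define EOT by eltrombopag.

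Three stronger readings are tempting but unsupported:
- **Every participant on CsA after eltrombopag is misreported by the full amount.** Closed records after EOT prevent this.
- **The CsA categories above 12 months are emptied.** Recorded end dates still fill them. The Week 52 visit also allows ±7 days, so an EOT at Day 372 is 12.2 months.
- **CsA dose intensity is biased.** Cumulative dose and duration may shrink together when an open record is cut, leaving their ratio much the same. No bias is shown.

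**Conclusion.** The rule is wrong as written for CsA and r-ATG. It gives too short a CsA duration for any participant with an EOT page and an open CsA record, mainly at the primary cut-off, and always in the same direction. The loss ranges from about a month, where records are closed monthly, to roughly 21% to 37% in the single-open-record case on the assumed dates. The number of participants affected cannot be found from the documents. Those still on eltrombopag at the cut-off have no EOT page, so their CsA is handled correctly by Scenario 1. The r-ATG error is large per case but probably rare.

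The primary endpoint does not use these dates, and the adverse-event on-treatment window is tied to eltrombopag. A reader might infer that the concomitant-therapy and laboratory windows, which run from the last study treatment date, also shrink. The SAP does not say that imputed dates feed that derivation, so this is possible but not shown. The point merits correction because the rule contradicts the trial's own definition of EOT, not because a main conclusion is at risk.

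**What to change.** Amend Section 5.1.1 in both SAPs:

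- **Eltrombopag:** keep the EOT date as the substitute.
- **CsA with no end date and not recorded as stopped:** use the earliest of the cut-off date, the Week 104 visit date, death and last contact. Otherwise use the last recorded CsA dosing date.
- **r-ATG:** use the last recorded infusion date.

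Do not cap imputed dates at the planned maximum duration, since that would overwrite real deviations. Do not rely on CsA dispensing data: Protocol 11.2 describes IRT tracking for eltrombopag only.

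The cost is a few lines of text in each SAP and one derivation program, using dates already planned for collection.
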